Hypothesis - What is the scientifically valid research question being asked?

Phase 1 pilot: As a pilot study we are not hypothesis testing, instead we are interested in acceptability and feasibility of providing the intervention by phone or videoconferencing instead of face to face. Feasibility is critical in terms of 1) recruitment ie whether we can recruit using on-line ie social media links to sports betting apps, Facebook, Instagram etc to recruit people who are having gambling problems either help-seeking (direct contact to SGTS) or not help-seeking 2) delivery of the intervention CET remotely ie uptake and completion of the therapy program

Phase 2 RCT: CET provided by phone and/or video conferencing will be more efficacious at reducing problem gambling and gambling behaviours including money lost than usual care of education and attention.

Aims - What do the investigators intend to achieve with this research project

Phase 1:

1. To evaluate whether we can use social media advertising to recruit 40 sports betting problem gamblers over 3 months who are either help seeking or not actively help seeking.
- 2 To deliver the CET intervention in up to 10 sessions by phone or video conferencing and determine the acceptability of this approach and the proportion who complete the intervention

Phase 2:

Evaluate whether CET delivered by phone or videoconferencing significantly reduces gambling behaviour compared to usual care of attention and education

Objectives - How will investigators achieve the aims of the research project?

Phase 1:

We will use paid advertising and informal i.e., study initiated social media and contacts with sporting clubs through the SA Office of Problem Gambling to advertise this research study. We have experience of delivering phone and on-line psychological interventions by phone and videoconferencing (HealthDirect) during the COVID pandemic for people presenting the FMC ED in crisis and providing IAPT or MyAPT successfully. We will build on this experience and the use of workbooks to guide a gambler through the treatment program.

Phase 2: to use the learnings from the phase 1 pilot to refine the recruitment of people who have problematic sports betting and deliver a randomised controlled trial nationally to determine if CET is efficacious at reducing gambling behaviour

Expected outcomes - What do the investigators anticipate the outcomes of this research will be?

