Outcomes will be pre - post quantified validated measures of gambling behaviour, anxiety and depression; feasibility and acceptability: ability to recruit people who are sports betting and acceptability of the intervention i.e., number of sessions attended and use of mobile phone and video conferencing to provide therapy. Pre and post outcome data will support existing evidence from our own and others trials to confirm the effect sizes and sample size for a larger phase 2 randomised controlled trial

Phase 2:

Use the learnings and effect size change in the CET group from phase 1 to implement a randomised controlled trial and recruit 140 people who provide consent and baseline data and test the efficacy of the experimental intervention (CET) versus control intervention.

Rationale / justification - How the research will fill any gaps and/or contribute to the field of research or contribute to existing or improved practice?

There are no proven treatments for sports betting internationally. This studies phase 1 and 2 would be the first beyond a case series that would demonstrate pre-post outcome measures to test a highly accessible psychological treatment for sports betting gambling disorder.

Research project setting - i.e. Where is the research being conducted i.e. FMC, GP Plus Marion, Noarlunga Hospital, Tonsley building, Sturt Campus, online forums and alternatives

Please ensure you list the site plus clinic/department / service.

The study will be based at The Flats – Flinders Psychological Therapy Services FMC site from where the therapists will deliver CET and usual care by phone or internet remotely to either SA or whole of Australia. Recruitment will occur for individuals across the whole of SA for phase 1 and all Australia for phase 2.

Methodological approach - clearly describe the specific procedures or techniques that will be used to answer the research question and meet the aims.

The intervention: in the published 6 cases treated by SGTS CET was provided face to face by experienced SGTS staff using a standardised workbook adapted for sports betting. The graded exposure-based approach identifies triggers which elicit a gambling urge and the person then systematically using homework tasks, grades their approach to each trigger until habituation of the gambling urge occurs. Ultimately all urges to gamble are extinguished and the person gains control over their gambling either through abstinence or occasional gambling.

Pilot trial phase 1 (SA)

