
Recruitment: 40 subjects to be recruited over a 3-month period in SA using social media, i.e., Facebook and Instagram to recruit on-line sports betting gamblers and through the OPG Gambling Help Services throughout SA.

Design: this would be a 12-month single arm trial with all participants being offered CET. Participants would receive up to 10 sessions (30-60 mins) provided over 2 months and follow up for another 3 months. We will recruit until we have 40 people who have provided signed consent forms and baseline questionnaires. All will be offered the intervention. As for all psychological interventions, of the 40, a proportion will not attend a single session (~5%), some will attend a single assessment only session (~10%) and others only 1 assessment and 1-2 therapy sessions (~20%) leaving about 65% who attend 4 or more sessions. (ie one assessment + 3 therapy sessions). This provides a naturalistic comparison group ie 35% of the sample who received no or minimal intervention compared to the intervention group (65%) who we will define as having 'an adequate dose' of the intervention. We will also conduct a per

protocol analysis of those who completed all 10 sessions to see the effect of the full dose of the intervention.

Phase 2:

140 subjects will be randomised to intervention (CET) or control ie usual care, in a 2-arm parallel 26 month randomised controlled trial, each arm receiving up to 10 sessions over 12 weeks delivered by phone and/or videoconferencing. Each participant will be followed for 12 months post intervention to determine outcomes of gambling behaviour, problem gambling severity, anxiety, depression and work and social adjustment.

Consumer and Community engagement – investigators are encouraged to consult with [Consumer and Community groups](#) with the design of their research. Please outline any consultation that has occurred.

SGTS has an active consumer group led by [name] a former client of SGTS who has recovered from a gambling addiction. He is employed 0.1FTE by SALHN to provide support to gamblers about to start treatment and during treatment. He has provided input to the design of the workbook and will be asked to continue his current role in contacting participants in the trial during their therapy to provide education and support as well as obtain feedback on the acceptability of the intervention.

What are your outcome measures?

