You should make a distinction between how you will recruit/select control participants compared to other groups if performing a comparative intervention.

How many participants will be selected for the study?

Phase 1 40

Phase 2 - 140

How are they identified as possible participants?

Help seekers who are sports betters who contact SGTS either through existing channels eg SGTS website or GP referral will be screened for eligibility and those non help seekers will be approached through advertising the study on social media ie Facebook, Instagram, and asked to provide contact details to the trial website (see below). A research assistant (RA) will then contact the participant to check eligibility and provide trial information.

Pre-screen for eligibility – waiver of consent

The recruitment method must be compliant with the Health Care Act 2008. If you need to access a patient's medical records to pre-screen for eligible participants, and you do not have prior patient consent to do so or are not part of the patient's clinical care team, you will need to apply for an exemption under 93(3)(f).

Are you requesting a waiver of consent to pre-screen?

No – I am part of the patient's clinical care team.

Yes

Under s93(3),(f) of the Health Care Act 2008, we wish to apply for an exemption of patient consent to access their personal information for research purposes. In order to identify suitable participants for this research project, <specify who or a title i.e. study coordinator> will be required to access <specify what is being accessed>, prior to obtaining consent from the patient.

How will participants be recruited into the study? Please provide a detailed step by step description of the recruitment methods i.e. flyers, adverts, direct approach, invitation letter etc.

Currently SGTS receives referrals from GPs, Gambling Help services and self-referral usually by word of mouth or the SGTS website. For this study, we will recruit from this source (help seekers) and for non-help seekers set up advertisements from Flinders University Facebook

and the University's links with Adelaide United football A League club (men and women) and Breakthrough Foundation links with the Adelaide Crows AFL club (men and women). The study advertising will be timed with a media story and the playing of A league and AFL games in Adelaide. In phase 1 this should be adequate exposure to recruit 40 people in the 3 month period.

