For phase 2 ie nationally, our links with the NSW Gambling Aware and Victorian Problem Gambling Foundation advertising and awareness campaigns will provide broad social media distribution and if those strategies are inadequate, we will use paid advertisements on Facebook, Instagram and Google adds linked to gambling , sports betting, sites or with words like 'gambling', 'sports betting', 'odds', 'bet', 'betting', 'stakes' etc as per <https://www.si.com/betting/2020/05/13/sports-betting-terms-definitions-gambling>.

How will they be approached? Which staff / research team members are approaching the participants? When is this occurring? I.e. clinic, inpatient.

The advertisement will read ' Are you worried about the amount of time or money you spend sports betting and want to help doctors to find out the best ways to help someone fix their gambling problem? ' If they click on this link they will be transferred to questions a) age 18 or older? b) resident in SA - postcode? For phase 2 the second question will be resident in Australia (postcode) ?

If yes to both, they will be transferred to the trial website on Redcap and asked to provide either or both their mobile phone or email address. The trial research officer will then use this information to contact them within 48 hours to explain the study and ensure they are eligible.

What are the inclusion and exclusion criteria? - Detail the characteristics that clearly describe the study population that are required to be either included or excluded in the research.

Inclusion: includes sports betting on any of the commercially advertised sports betting gambling sites at least once per month e.g., Sports bet and losing amounts that the person believes is excessive or time spent is excessive, willingness to have counselling sessions recorded and to provide follow-up data, age greater than 17, access to a smart phone and or internet. Receiving or having received psychological treatment for a gambling problem in the last 12 months is not an exclusion.

Exclusion: mental distress e.g., psychosis or suicidality so as not to be able to give informed consent. Concurrent other forms of gambling e.g., pokies, TAB or lotto are acceptable as are co-morbidities of depression, anxiety and other addictions e.g., alcohol or tobacco.

Participant commitment -What will their participation involve? I.e. study visits, procedures, tests, tissue samples, questionnaires, wearing of any devices.

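### Phase 2 eligibility does not bar Phase 1 participants or people currently receiving CET, so some could be randomised to the education control and dilute the contrast

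*Protocol*

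**What the plan says.** The protocol gives one set of criteria, under *What are the inclusion and exclusion criteria?*, with no separate list for Phase 2. On previous and current treatment it is explicit: "Receiving or having received psychological treatment for a gambling problem in the last 12 months is not an exclusion". The only exclusion is "Exclusion: mental distress e.g., psychosis or suicidality so as not to be able to give informed consent". To be included, a person must bet on sports at least monthly and regard the losses or the time spent as excessive.

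Four other places bear on who could enter Phase 2:

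- *Pilot trial phase 1*, Design: "this would be a 12-month single arm trial with all participants being offered CET". The target is 40 people.
- *Research project setting*: "Recruitment will occur for individuals across the whole of SA for phase 1 and all Australia for phase 2". The Phase 2 catchment therefore contains the Phase 1 catchment.
- *Methodological approach*: "in the published 6 cases treated by SGTS CET was provided face to face by experienced SGTS staff". SGTS already provides this therapy for sports betting.
- *How will participants be recruited into the study?*: "Currently SGTS receives referrals from GPs, Gambling Help services and self-referral usually by word of mouth or the SGTS website". The protocol then names this stream as its source of help seekers.

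The Phase 2 hypothesis is that CET "will be more efficacious at reducing problem gambling and gambling behaviours including money lost than usual care of education and attention". *Matching and sampling strategies* stratifies Phase 2 on type of gambling only. *Accounting for potential bias* relies on participants not knowing the study hypothesis and on therapists not naming the alternative treatment. The primary outcome, the Victorian Gambling Screen (VGS) harm-to-self subscale, is rated by the participant.

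**The concern.** Phase 2 compares CET with a workbook of education and monitoring that contains no exposure therapy. Two kinds of entrant blur that comparison, and the criteria admit both.

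The first is someone receiving CET elsewhere, for example at SGTS, at the time of randomisation. If allocated to control, that person has the experimental therapy during the trial.

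The second is a Phase 1 participant. If allocated to control, that person may still use what was learned. If allocated to CET, that person is repeating a therapy that may add less the second time. Either way the expected difference between arms shrinks.

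Masking is also affected. A Phase 1 participant has been told that CET was the therapy under study, and the protocol plans to tell Phase 1 participants that their contribution helps prepare the larger study. In Phase 2 such a person could recognise which arm is experimental. With a self-rated primary outcome, this weakens the safeguard against self-report bias.

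This is a rule the protocol states, not a detail left open for an analysis plan. The eligibility call made by the research assistant would not catch these people, because it checks against criteria that admit them.

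**Working it through.** **1. Can the text lead to this?** Current or recent gambling treatment is expressly allowed. The single exclusion concerns capacity to consent. Phase 1 offers CET to everyone. Phase 2 includes South Australia. SGTS is both a provider of CET and a recruitment source. No section bars Phase 1 participants, sets a wash-out or treats CET differently from other therapy. So yes: following the text, a Phase 1 participant or a current CET client could be randomised to control.

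**2. Reproduce the planned sample size.** Inputs from *Sample size and statistical or power issues*: two-sided alpha 5%, power 90%, SD 10.2, difference 4.8 points (8% of the 60-point range), r = 0.7, 50 per group. Taking r as the correlation between baseline and follow-up in a baseline-adjusted comparison:

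- Adjusted SD = 10.2 × √(1 − 0.7²) = 10.2 × √0.51 = 7.284.
- n per group = 2 × (1.960 + 1.282)² × 7.284² / 4.8² = 48.4, rounded up to 49.

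This matches the stated 50 closely. The planned power thus rests on the full 4.8-point difference, with no allowance for dilution.

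**3. Power as planned, 50 evaluable per group.**

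- SE = 7.284 × √(2/50) = 1.457.
- Power = Φ(4.8 / 1.457 − 1.960) = Φ(1.335) = 90.9%.

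**4. Illustrate dilution.** Let f be the share of Phase 2 entrants with current or previous CET, and k the fraction of the between-arm contrast lost in them. The protocol states neither; both are assumptions. Then:

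- Expected difference = 4.8 × (1 − f × k).
- Power = Φ(expected difference / 1.457 − 1.960).

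| Share f | Difference, full loss (k = 1) | Power | Difference, half loss (k = 0.5) | Power |
|---|---|---|---|---|
| 0% | 4.80 | 90.9% | 4.80 | 90.9% |
| 5% | 4.56 | 87.9% | 4.68 | 89.5% |
| 10% | 4.32 | 84.3% | 4.56 | 87.9% |
| 20% | 3.84 | 75.0% | 4.32 | 84.3% |

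**5. What Phase 1 alone could supply.** All 40 participants would be 40/140 = 28.6% of Phase 2. The protocol itself expects about 35% of them to receive no or minimal therapy. That leaves 0.65 × 40 = 26 with what it calls an adequate dose, or 26/140 = 18.6%. Even this would need every one of the 26 to qualify again and enrol again. It is an upper bound from this route, not a forecast. SGTS clients are a further route, of unstated size.

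**The case against.** The strongest objection is that eligibility itself limits the problem. An entrant must still be betting monthly and regard the losses or time as excessive. People for whom CET worked would mostly not qualify. Those with earlier CET who do qualify would mainly be relapsers, non-responders or early drop-outs, in whom carry-over is weakest, and baseline adjustment absorbs part of any benefit already visible at entry. This stands. It makes full loss of contrast an extreme case and argues for a small share. It does not help with someone receiving CET at the time of randomisation, and it does not restore the masking.

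The broad criteria also look deliberate: the protocol equally accepts mixed gambling and several co-morbidities. A wide population is a legitimate choice. It does not require admitting people who are having the experimental therapy itself. Phase 2 is still prospective and has national recruitment channels, so heavy overlap is speculative; that too is fair.

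Several stronger readings are tempting, and the document does not support them:

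- *Prior treatment in this population is usually CET.* No frequency is given, and SGTS has also used cognitive therapy.
- *The effect of CET lasts.* The protocol describes urges being extinguished and control being gained, but says nothing about duration.
- *The arms will be unbalanced on earlier CET.* Randomisation is 1:1 in permuted blocks, which balances it in expectation. Not stratifying on a factor is not the same as imbalance.
- *Some 29% of Phase 2 could be affected.* That ignores the expected low uptake in Phase 1 and the need to qualify again.

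**Conclusion.** The point holds in a limited form. The criteria as written allow a Phase 1 participant or a current CET recipient to be randomised to the education control, and nothing else in the protocol prevents it. The consequence is a diluted treatment contrast and weaker masking to the hypothesis, not a confounded comparison.

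Its size cannot be established from the document. If the share is 5% to 10%, the loss of power is about 1 to 7 percentage points, depending on how much contrast is lost; at 20% it is about 7 to 16 points. These figures assume 50 evaluable per group, baseline adjustment with r = 0.7, and dilution proportional to the share exposed. The betting and excessive-loss criteria push towards the lower end. The case for changing the text rests on how cheaply the gap can be closed, not on a demonstrated large loss.

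**What to change.** Add to the Phase 2 eligibility criteria an exclusion for (a) anyone enrolled in Phase 1 and (b) anyone currently receiving CET or other exposure-based gambling therapy from any service. Check both at the eligibility call that the research assistant already makes. State that other past gambling treatment remains eligible, which keeps the broad population the protocol appears to want.

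The Phase 1 bar should be separate and without a time limit. Phase 2 funding is still to be sought, so a bar tied to a recent-treatment window could lapse before recruitment starts.

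A wider exclusion of all exposure therapy in the last 12 months is a debatable trade-off and is not needed here. Whether to adjust for previous treatment, or to report subgroups by it, can be left to the statistical analysis plan.

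The cost is a sentence in the criteria and one or two questions at an existing call. A small number of people, mainly South Australian and SGTS clients, become ineligible for a nationally recruited trial.

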Gambling disorder has devastating consequences for the gambler and up to 7 others (Productivity Commission 2010) with not only financial ruin but loss of occupation, family and sometimes incarceration. In two of our prison studies 55-70% of inmates had a lifelong gambling disorder. The interventions we have developed at Statewide Gambling Therapy Service (SGTS) and Flinders University over the last 20 years began with people addicted to pokies using cue exposure (behavioural) therapies (CET) and the addition of cognitive therapy. We have refined and adapted this model for all forms of gambling most recently sports betting. Having a proven effective therapy delivered remotely over 6-10 sessions would be a breakthrough in Australia and world-wide. Flinders and SGTS could become the centre of this form of therapy for sports betting and any other form of on-line gambling internationally. Careers, families and lives would be saved.

This phase 1 pilot proposal aims to recruit 40 participants from all areas of SA and provide CET using mobile phone or internet in contrast to those who have received the intervention from SGTS face in a clinic setting as described in the published 6 case studies. This would provide the data to inform a phase 2 national randomised controlled trial with funding sought from other states and/or NHMRC Partnership grant.

Phase 2 RCT: Partners will be sought from SALHN, SA DHS, Victorian and NSW Problem Gambling Foundation (Vict) and Gambling Aware (NSW) and other state and territory gambling

help service funding bodies towards a national randomised controlled trial (RCT) aiming to randomise 140 sports betting individuals across Australia. Participants will be randomised to either CET or usual care – a therapist delivered on-line/phone educational and motivational workbook to provide equivalent attention.

Significance

This study provides a state-of-the-art digital intervention for the treatment of sport betting and other internet-based addictions. It addresses the Office of Problem Gambling, SA government's responsibility and commitment to reduce the effects of problem gambling in SA and potentially apply this to the rest of Australia and internationally. As problem gambling disproportionately affects lower socio-economic groups including our indigenous population this intervention addresses the University's values and strategy in prioritising socially disadvantaged populations

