The RA will contact the person to arrange a suitable time to go through the trial information, providing the patient information and consent form (PICF) electronically. If the person gives consent, they may sign this form electronically and return it electronically or print and scan or

print and post the form. They will also be asked to complete the baseline questionnaires at this or a subsequent session. These are returned as above. Once the questionnaires are completed the RA will arrange for the trial therapist to contact the person to commence CET (phase 1).

For phase 2, at this point the RA will contact the Clinical Trials centre to obtain the randomisation allocation. They will then provide the appropriate therapist information to contact the person to commence the first therapy session.

Intervention: CET. The first session includes asking the person to put Money Management in place ie ceasing or pausing credit card/phone/efpost access, cancelling phone and internet gambling accounts, arranging for a daily or weekly allowance managed by a significant other. All participants are given a standardised treatment rationale during their first session and checked if they agree to proceed with the treatment plan. They are also helped to define a problem statement and end of treatment goal. They receive a standard mental health and CBT assessment screening for co-morbid psychiatric disorders and risk to self or others.

The CET treatment is delivered in individual sessions and conducted according to a detailed manual which is adapted from one used previously in a randomised control trial ([name] et al. 2015). Treatment comprises up to 10 weekly 30-60-min sessions, though participants may have receive fewer or a greater number of sessions depending on the pace at which they moved through their graded cue exposure hierarchy.

During the second session an initial hierarchy of gambling cues is developed which is altered according to the clients' insights and responses throughout

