treatment. This is a collaborative process between therapist and participant and utilised cues such as their smartphone, images of sports betting websites and preferred sports, and videos of sporting matches. Exposure is graded up to watching a live sporting match online or on the television while holding a smartphone with betting account credits and habituating to the urge to gamble. For mixed gamblers, habituation tasks also include in vivo (live) exposure in a gambling venue holding money and habituating to the urge to gamble. Clients are encouraged to perform CET homework regularly between session. Once participants extinguish their urge response from a cue, they moved to the next task on their graded hierarchy.

Control (phase 2): Usual care: Up to 10 sessions described in a workbook will be provided of 30-60 minutes duration consisting of education about gambling risks and harms, the technology and psychology of gambling, skill vs computer algorithms which favour the gambling company, the psychology of intermittent reinforcement. Participants will be asked to monitor their gambling cognitions, gambling time and money spent/lost through use of a monitoring diary and assisted to set life recreational goals as alternatives to gambling.

All participants will be asked to complete questionnaires, provided on-line via email at the beginning of each treatment session as per usual care for gambling clients taking 10-15 minutes ie Gambling time and money spent, PHQ-9 depression (q 9 to check for suicidal behaviour), GAD7 anxiety and additional questionnaires as above at baseline (30-40 minutes), session 4, end of treatment session 10 and 2 month post treatment follow up (phase 1) and 3 month and 12 month post treatment (phase 2) .

For phase 1, 6 participants and 6 significant others will be asked to participate in a semi-structured interview of 15-30 minutes of the acceptability and feasibility of the recruitment process and intervention.

Participant follow up – how are participants monitored during the study?

Participants are followed up weekly at each therapy session and at 2 months follow up (phase 1) by the therapist both from use of questionnaire data and phone or video observation and clinical contact and for phase 2, at 3 and 12 months post treatment by the RA.

All participants are monitored through the clinical on-line data collection system PC-MIS and weekly therapist supervision sessions provided by CIs, [name], [name] and [name]

Consent

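### For Phase 2 the protocol limits each arm to 10 sessions but elsewhere lets CET run beyond 10, which is at odds with a control meant to match therapist attention

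*Protocol*

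**What the plan says.** Four places in the protocol bear on the number of sessions in Phase 2.

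- *Methodological approach*, Phase 2 design: "each arm receiving up to 10 sessions over 12 weeks delivered by phone and/or videoconferencing".
- *Participant commitment*, CET: "Treatment comprises up to 10 weekly 30-60-min sessions", followed directly by "though participants may have receive fewer or a greater number of sessions depending on the pace at which they moved" through the hierarchy of gambling cues. No maximum is attached to the larger number.
- *Participant commitment*, Phase 2 control: "Up to 10 sessions described in a workbook will be provided of 30-60 minutes duration". Nothing provides for more than 10.
- *Background and literature review*, Phase 2 RCT: usual care is described as a "therapist delivered on-line/phone educational and motivational workbook to provide equivalent attention". The *Hypothesis* section says CET will be more efficacious "than usual care of education and attention".

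*Participant commitment* also lists the questionnaire points for all participants, one of which is "end of treatment session 10".

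**The concern.** The control is there so that a Phase 2 difference can be attributed to exposure rather than to time spent with a therapist. That requires the two arms to work under the same contact rule. The design statement gives them one, but the CET description relaxes it for CET only. Randomisation does not remove such a difference, because it would be part of what the assigned arm delivers. An intention-to-treat comparison would then set CET plus any additional contact against attention that stops at 10 sessions.

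There is a secondary effect on assessment. One questionnaire point is identified both as the end of treatment and as session 10. For a CET participant who goes on to session 11 these are different occasions, and the protocol does not say which one counts.

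**Working it through.** The check is mainly a comparison of texts. The sample size calculation does not enter it.

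**Step 1: the session rules side by side**

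| Place in the protocol | CET, Phase 2 | Control, Phase 2 |
|---|---|---|
| Phase 2 design statement | at most 10, over 12 weeks | at most 10, over 12 weeks |
| Arm description | 10, but fewer or more according to pace; no ceiling | at most 10; no extension |
| Length of session | 30 to 60 minutes | 30 to 60 minutes |
| Purpose of control | – | same attention as CET |

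The first two rows agree for the control and disagree for CET.

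**Step 2: does the CET clause apply to Phase 2?** It is not restricted to Phase 1. The CET description comes after the Phase 2 randomisation step and before the Phase 2 control, and it is the only session-level account of how CET is delivered.

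**Step 3: planned maximum contact.** Contact is sessions × minutes per session.

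- Both arms under the design statement: 10 × 30 = 300 minutes to 10 × 60 = 600 minutes.
- Control under its own description: the same, 300 to 600 minutes.
- CET under its own description: no maximum can be computed, because no ceiling is given.

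**Step 4: illustration for one participant.** Assume weekly CET sessions from day 0 that fill the 12-week (84-day) window. Session *k* falls on day 7 × (*k* − 1), so session 10 is on day 63 and session 12 on day 77. Twelve sessions give 12 × 30 = 360 to 12 × 60 = 720 minutes. The ratio to the control maximum is 12/10 = 1.2, or 20% more. That is 2 extra sessions, 60 to 120 minutes.

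**Step 5: from one participant to the arm.** The difference in mean sessions depends on the share of CET participants who exceed 10, by how many, and the shares in each arm who have fewer. None of these is in the protocol. As an assumption only: if 10% of CET participants had 2 to 3 extra sessions, the CET mean would rise by 0.10 × 2 = 0.2 to 0.10 × 3 = 0.3 sessions. If another 10% finished 2 sessions early, the change would be −0.10 × 2 = −0.2, which cancels the lower figure. The sign of the net difference is therefore not determined by the text.

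**The case against.** The strongest reply is that one clause stands against an otherwise consistent plan. The Phase 2 design statement, the control description and the session-10 questionnaire point all use 10, and so does the opening of the CET sentence itself. The clause is in an uneven past tense, in a paragraph about a manual adapted from an earlier trial, so it may be carried-over text. That is plausible but cannot be shown from the protocol. The clause remains operative, and a CET therapist reading it would take it as permission to continue.

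A reader might infer more than the text supports, in four ways.

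- *Contact is confounded with treatment.* The text makes an imbalance possible but does not establish one. Both arms may have fewer than 10 sessions, and faster CET participants could have less contact than controls.
- *The extra sessions go to people who are not improving.* The protocol refers to pace through the hierarchy. Slow pace is not the same as a poor result on the Victorian Gambling Screen.
- *CET participants would still be in treatment at the 12-week assessment.* The clause relaxes the number of sessions, not the 12-week window. Twelve weekly sessions fit inside that window, so this would need a further departure from the plan.
- *The 20% is the difference between arms.* It is a figure for one participant under an assumed schedule.

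It is also fair to say that Phase 2 is still to be funded and is to be refined from the pilot, and that a table of sessions by arm may already be in an analysis plan that was not available. What stands is the contradiction and its conflict with the stated purpose of the control. An analysis plan cannot undo a contact difference that arises in delivery.

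**Conclusion.** The concern holds for Phase 2. The protocol contradicts itself on whether CET may exceed 10 sessions, and as written only CET can. The text therefore permits contact to differ by arm, against the claim of matched attention. It also leaves open when the session-10 questionnaires are given to a CET participant who continues.

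The size and net direction cannot be computed. The only figure available is illustrative: 20% above the control maximum for one participant with 12 weekly sessions. It rests on the assumption that weekly sessions fill the 12-week window. Phase 1 has one arm and so no between-arm imbalance. The point should be settled before Phase 2 starts, because it is a matter of wording now and could not be corrected after delivery.

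**What to change.** Reconcile, for Phase 2, the design statement, the CET description, the control description and the attention claim in the background. The session limit and any provision for extension should be stated consistently for both arms. Which rule to adopt is for the sponsor. State which occasion carries the end-of-treatment questionnaires if a participant can continue past session 10.

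Report sessions attended by arm. If a CET-only extension is kept, remove the statement that the control is there "educational and motivational workbook to provide equivalent attention", and limit the conclusion to CET including any additional contact.

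The cost is wording in four places and one by-arm table. Attendance should be countable, since questionnaires are completed at the start of each session and all sessions are audio recorded. The protocol does not say that therapist minutes are logged, so the request is for session counts.
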